Since rigorous studies implementing a VLCD in youth with T1D remain to be done, the present pilot study is being undertaken to evaluate the glycemic and metabolic changes that accompany initiation of a very low carbohydrate diet in adolescents and young adults with T1D who are receiving insulin pump therapy. Specifically, we will measure changes in plasma glucagon, β -hydroxybutyrate, and free fatty acid (FFA) levels, as well as changes in basal hepatic glucose production, glycerol turnover, lipid oxidation and plasma glucagon responses to arginine infusions. Continuous glucose monitoring will be used to evaluate changes in plasma glucose responses to meals before and after initiation of the VLCD. Insulin pump downloads will be employed to assess changes in basal and bolus insulin doses.

Aims: To examine changes in sensor glucose levels, basal and bolus insulin doses, and FFA, glucagon, and β-hydroxybutyrate levels following implementation of a VLCD. Sensor-derived time glucose ranges will serve as a surrogate marker of hemoglobin A1c given the short duration of the study. We will also be assessing safety measures of the diet, including daily fasting ketone levels. Hypothesis: We hypothesize that use of a VLCD with strict monitoring of ketosis will reduce glycemic variability and increase time in target range, defined as 70-180 mg/dL by reducing the time in the hyperglycemic (>180 mg/dL) and hypoglycemic ranges (<70 mg/dL). Decreased carbohydrate intake will lead to less postprandial hyperglycemia. Lower insulin doses for meals and snacks as a result of decreased carbohydrate intake will lessen postprandial hypoglycemia as well.

Further, we will also measure changes in glucose and glycerol metabolic fluxes using stable isotopes and indirect calorimetry to measure rates of fat oxidation before and after 2 weeks of a VLCD. Arginine infusion will used to assess changes in plasma glucagon responses with the VLCD. Hypothesis: Glucose and glycerol turnover will be increased in those with T1D on a very low carbohydrate diet. Lipid oxidation will also be increased. We further hypothesize that the arginine-stimulated glucagon response will be increased while on the VLCD will, in turn, decrease the risk of late post-meal hypoglycemia during the VLCD.

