Research Plan: This prospective feasibility study of 10 youth (ages 13 – 25) with T1D will evaluate glycemic and metabolic changes after 2 weeks of a high protein VLCD compared to 2 weeks on a standard carbohydrate diet (see Table 1). The study will take place in 2 parts. Part 1 will only involve the high protein VLCD, but part 2 will involve high protein VLCD and high fat VLCD's.

| Type of Diet | Carbohydrates | Protein | Fat |
|-------------------|---------------|---------------|---------------|
| Standard | 25%+ | Not specified | Not specified |
| Carbohydrate | | | - |
| High Protein VLCD | 11% | 54% | 35% |
| High Fat VLCD | 11% | 23% | 66% |

Table 1. Types of study diets and macronutrient content in each planned diet.

Part 1: First, to evaluate the feasibility of following a high protein VLCD, participants will follow a standard carbohydrate diet for 2 weeks, followed by a 1 week transition to a VLCD, and then follow the a high protein VLCD for 2 weeks. The study will consist of 3 in person or virtual visits which will take place over ~5 weeks. All participants will be initially studied for 2 weeks while ingesting a standard diet recommended by the American Diabetes Association, followed by a 1-week transition to a VLCD, and followed by 2 weeks on the high protein VLCD. During the first (baseline) period fasting β -hydroxybutyrate levels will be measured 2-3 times per week. During the VLCD study periods, fasting β -hydroxybutyrate levels will be measured daily in the morning using a blood ketone meter; insulin doses will be collected using insulin pump downloads and continuous glucose monitoring (CGM) profiles will be used to assess glycemic excursions on each diet, as

[figure not shown]
Page **3** of **26**

well as the time in hypo-, eu- and hyperglycemic ranges. Part 1 of the study is anticipated to be complete by December 31, 2022.

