5. **Participants**: This study will enroll 10-20 participants (ages 13 to 25) with T1D. At least 4 adults over the age of 18 will be enrolled. Ten youth will be involved in Part 1, which evaluates feasibility of the diet. If those youth would like to continue to Part 2 of the study they may continue, or they will be replaced by new participants. To be eligible for inclusion, the participant must have T1D for at least 1 year, have an A1c between 6.5% to 10.0% inclusive, and BMI of at least 19 kg/m2 (or 5th percentile for those under age 18) and be willing to wear a CGM, which is the currently recommended standard of care for children with type 1 diabetes and is FDA approved for use above age 2 years. They must also be willing to adhere to a VLCD, measure β -hydroxybutyrate levels daily and to keep a detailed food diary. Participants who are unable to wear a CGM, monitor their diabetes control or maintain the VLCD will be replaced.

Study visits: Participants will be recruited from Yale Pediatric Diabetes Center and Yale Diabetes Center clinics, as well as through social media. All participants will undergo pre-screening of their electronic medical record (or faxed medical record from their pediatric endocrinologist or endocrinologist) to evaluate study eligibility by review of medical history, as well as prior physical exams and laboratory tests. No blood will be collected in part 1 of the study.

Figure 1. Timeline of visits and telephone follow ups for the duration of the study. Visits and calls may be modified depending on patient availability and academic schedule. Part 1 of the study will involve in-person or virtual visits (Facetime, Video Doximity Calls, Zoom, or Skype) and telephone study visits. Part 2 of the study will involve in-person visits.

Screening & Enrollment Visit 1: Screening will be conducted by invitation to potentially eligible subjects. For the first part of the study, the study will be explained and telephone or e-consent will be obtain prior to conducting any study procedures. Participants will 1) meet in person or 2)use telephone to discuss the study or 3) Skype, Zoom, FaceTime or Doximity Dialer enabling video calls. Scales will be provided for all participants.

Consent: Consent will be transitioned to an online/electronic format using the YSM version of REDCap if consent is not obtained in person.

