- Anthropometric measures will be reviewed from the most recent clinic visit, including height, weight, BMI, vital signs). Participants will self-identify their tanner stages based on gender-specific norms.
- Current diabetes care practices (frequency of self-monitored blood glucose (SMBG), insulin dosing, review of blood glucose values)
- Medical History: duration of diabetes, comorbidities, past medical history, social history, family history, medications, and allergies.
- Additional diabetes history including current/past use of CGM, insulin pump, and other modes of diabetes technology.
- Frequency of missed school days and Emergency Department visits due to decompensated diabetes (i.e., hyperglycemia, ketosis and DKA) over the past 6 months
- Questionnaires will be administered, including:
 - a. Diabetes Treatment Satisfaction Questionnaire (DTSQ), which includes eight items, six of which form a scale (scored 0-36) in which higher scores indicate greater treatment satisfaction (Bradley, 1994).
 - b. Nutrition Knowledge Survey (NKS) which collects information on healthful eating, carbohydrate counting, blood glucose response to foods, and nutrition label reading. Higher NKS scores reflect greater nutrition knowledge (score range is 0–100%) (Rovner 2012).
 - c. Diabetes Distress Scale (DDS) is a 17-item scale that captures diabetes distress in 4 different areas, including emotional burden, regimen distress, interpersonal distress, and physician distress (Polonsky 2005).

Page 5 of 26

PI: [name]

All participants will receive dietary instruction to review the dietary requirements of the study. A handout with examples of the type of diet required will be provided to each participant at the time of or prior to consent. Participants will provide a 3-day dietary history at the enrollment visit to assess current caloric intake. Each subject will be instructed on how to keep a food diary. Participants and/or parents will be asked to take photos of all food consumed to aid in dietary recall. After the enrollment visit, participants will be contacted to assess adherence to the diet and adjust insulin doses 3 times per week (see Table 1). During these telephone follow up calls, food diary will be reviewed, photos of meals will be reviewed, and pump and CGM data will be uploaded and reviewed. Participants will receive a link in their email to fill out the 3 surveys using Yale Qualtrix.

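### No eligibility criterion excludes people already eating below the standard diet's 25% carbohydrate floor, so some paired differences could reflect a return to low carbohydrate rather than its initiation

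*Combined protocol and SAP*

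**What the plan says.** **Aim.** Section I, item 4 (Background) says that the pilot is meant to "evaluate the glycemic and metabolic changes that accompany initiation of a very low carbohydrate diet" in adolescents and young adults with type 1 diabetes.

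**Sequence.** The Research Plan puts the comparator first: "All participants will be initially studied for 2 weeks while ingesting a standard diet". A one-week step down and two weeks on the VLCD follow. Part 2 repeats this order.

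**Comparator.** The diet table in the Research Plan (Table 1) gives it as "Standard | 25%+ | Not specified | Not specified". The text also calls it "a standard diet recommended by the American Diabetes Association", without a figure.

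**Eligibility.** Item 5 says of diet: "They must also be willing to adhere to a VLCD", and asks for a detailed food diary. Item 9 adds willingness to log diet. The other criteria concern age, BMI, insulin treatment and CGM use, A1c, recent ketoacidosis, other drugs, psychiatric and eating disorders, pregnancy and other illness; item 5 adds diabetes duration. None refers to usual carbohydrate intake.

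**Information on usual diet.** For both parts: "Participants will provide a 3-day dietary history at the enrollment visit to assess current caloric intake". No eligibility or analysis rule uses it.

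**Analysis.** Item 13 plans paired t-tests of the CGM measures between the two diets, with no reference to pre-study diet. Meal content comes from ASA24, and macronutrient content is to be reported by diet.

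**The concern.** A before-and-after comparison measures initiation only if the first period resembles the participant's starting state, or at least does not move them away from it in the direction the second period reverses. For a person who habitually eats below 25% carbohydrate, the standard weeks raise intake and disturb settled insulin dosing, and the VLCD weeks then restore the usual pattern. The resulting difference answers another question: what happens when low carbohydrate eating is interrupted and resumed.

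Feasibility, the stated purpose of Part 1, is also affected. Completing two weeks on a familiar diet says little about whether a newcomer can do so, and item 5 replaces participants who cannot maintain the VLCD.

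**Working it through.** The plan gives no power or sample-size calculation, so there is no figure to reproduce. The check puts the diets on one scale and follows one person through the schedule.

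**1. Energy scale.** Visit 2 (Part 1) and the matching Part 2 text equate 20% carbohydrate with about 100 g/day. At 4 kcal per gram (assumed), implied energy is 100 × 4 / 0.20 = 2000 kcal/day. A range of 1600 to 3000 kcal is shown below as an assumption.

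**2. The floor in grams.** 0.25 × 2000 / 4 = 125 g/day (100 to 187.5 g over the range).

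**3. One habitual low carbohydrate eater.** Take someone at 50 g/day, the upper limit of a VLCD as defined in the Background. At 2000 kcal this is 50 × 4 / 2000 = 10% of energy. Nothing in items 5 or 9 excludes this person if A1c lies between 6.5% and 10.0%. To follow the standard diet they must add at least 125 − 50 = 75 g/day. The VLCD weeks then take them back towards where they began. If they do not raise intake, the standard period falls below its own definition and the two periods differ little.

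**4. Weight in the result.** With k such people among 10, an initiation effect D in the others and a difference R in these people, the expected mean is (1 − k/10) × D + (k/10) × R. The shift from D is (k/10) × (R − D), or 10% of the gap per person. The documents give none of k, D or R. With D assumed to be 5 points of time in range:

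| k | R (assumed) | Mean | Shift relative to D |
|---|---|---|---|
| 0 | any | 5 | 0% |
| 1 | 20 | 0.9 × 5 + 0.1 × 20 = 6.5 | +30% |
| 2 | 20 | 0.8 × 5 + 0.2 × 20 = 8 | +60% |
| 2 | 5 | 5 | 0% |
| 2 | 0 | 0.8 × 5 + 0 = 4 | −20% |

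The table shows only that the sign and size depend on unknowns.

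**5. Smallest contrast the plan permits.** This is a separate matter, set by the VLCD target rather than by eligibility. The diet table has "High Protein VLCD | 11% | 54% | 35" (percent carbohydrate, protein, fat); the visit text has other figures.

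| VLCD target | Gap from the 25% floor at 2000 kcal | 1600 to 3000 kcal |
|---|---|---|
| 11% (Table 1) | 14 points: 0.14 × 2000 / 4 = 70 g/day | 56 to 105 g |
| About 50 g/day (adults, visit text) | 125 − 50 = 75 g/day | 50 to 137.5 g |
| 20% (adolescents, visit text) | 5 points: 0.05 × 2000 / 4 = 25 g/day | 20 to 37.5 g |

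If the adolescent limit is read as 100 g at 1600 kcal, it equals 100 × 4 / 1600 = 25%, and the permitted gap is zero.

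**The case against.** Four points deserve weight.

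- **The assigned standard period is a common reference.** A habitual low carbohydrate eater who follows it still contributes a comparison of VLCD with standard diet. A reader might infer that the effect of starting a VLCD is not measured at all. The documents do not support that: the problem belongs to the affected participants and to how their difference is interpreted.
- **The A1c floor is a partial screen.** The Background reports that adults with type 1 diabetes on these diets reach normal A1c, so on the protocol's own premise many successful users would be excluded at 6.5%. This stands, but a low carbohydrate eater with A1c inside the range remains eligible.
- **Enrolment of such people is possible, not shown.** Social media recruitment and the cited observational study of 131 children on a VLCD might suggest that it is likely. Neither says who will enrol here.
- **Diet is closely watched.** Diaries and photos are reviewed three times a week, insulin is adjusted, and a dietician reviews each person's standard-week intake. This would reveal the problem and may soften it. However, the only stated use of the dietician's review is to set the transition-week target.

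A reader might also infer that the two diets barely differ, perhaps because the 75–125 g transition band reaches the 125 g floor. The transition week is not an assessment period, and the gap is at least 14 points under Table 1 and about 75 g/day for adults at 2000 kcal. Only the adolescent wording of the visit text permits a narrow contrast.

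**Conclusion.** The gap is real. Following the plan exactly, a person already below the comparator's 25% floor could enrol, and their paired difference would not represent initiation of a VLCD. Familiarity with the diet could also overstate feasibility. Each such person carries 10% of a 10-person mean.

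A reader might go further and infer that benefit is exaggerated. The documents do not support this: how many such people would enrol, and how their response would compare with that of newcomers, are both unknown, so neither the direction nor the size of any bias can be stated. The point is a mismatch between the stated aim and who may enter, worth closing because the remedy is cheap.

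The narrow adolescent contrast (5 points, or 25 g/day at the implied 2000 kcal) is a separate inconsistency in the VLCD definition. An eligibility change does not cure it.

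**What to change.** 1. **Item 9, both parts.** Exclude habitual carbohydrate intake below 25% of energy, judged from the 3-day dietary history already collected at enrolment. State that the history is read for carbohydrate as well as calories. For anyone continuing from Part 1, apply the criterion to the Part 2 history.
2. **Item 13.** List each participant's achieved carbohydrate intake in both periods from the planned ASA24 data. Show the CGM results for all participants and again without anyone whose standard-period intake was below 25%.
3. **Separately, reconcile the VLCD carbohydrate descriptions.** These are 50 g/day or less in the Background; 11% in Table 1; and, in the visit text of both parts, under 20% or about 100 g/day for adolescents and under about 50 g/day for adults. Which figure applies is for the sponsor to settle.

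**Cost.** One criterion, one listing and one extra display, with no new visit or measurement. A few willing volunteers become ineligible.

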Data from the Diabetes Control and Complications Trial (DCCT) demonstrated that lowering the A1c by intensive insulin management to near-normal glycemic levels decreases the risk of complications related to diabetes (6). However, intensive management in the DCCT was accompanied by marked increases in severe hypoglycemia and more recent data have implicated increased insulin doses as risk factors for cardiovascular disease in T1D (7). One approach to achieve targeted glycemic control with less insulin exposure is through the use of a very low carbohydrate diet (VLCD), defined as limiting carbohydrate intake to 50 grams per day or less (8). In adults with T1D, these diets have been shown to achieve exceptional glycemic control with physiologically normal A1c values with lower total daily insulin doses due to decreased mealtime insulin for low amounts of carbohydrate intake (9, 10).

Importantly, VLCDs have not been formally studied in adolescents and young adults with T1D. Observational data on children using a VLCD are also conflicting. A small case series of 6 children with T1D on a low carbohydrate diet showed deficits in anthropomorphic measurements and elevated lipids, though in some cases a caloric deficit was also reported (11). Conversely, a recent observational study of 131 children with T1D on a VLCD reported no significant change in height percentile or SDS after initiating the diet (12). Prior studies have explored use of low carbohydrate diets in T1D, but none have specifically monitored for ketosis. In those studies, it is likely that the lack of carbohydrate intake led to lower insulin needs, thus increasing lipolysis and ketogenesis, and levels of ketosis while on this type of diet require further study (13).

Page 2 of 26

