Visit 2: After 2 weeks on the standard carbohydrate diet, insulin pump and CGM data will be uploaded (Tidepool, Dexcom, Medtrnoic, Omnipod or Tandem site, depending on the insulin pump being used) and reviewed. Dose adjustments will be made as clinically indicated. Participants will receive a link in their email to fill out the 3 surveys using Qualtrix.

The dietician will look at each individuals macronutrient intake during the standard carbohydrate portion of the study. Based on this information, we will instruct them to eat a certain amount of carbohydrates each day. If they eat more than 200 grams per day of carbohydrates during the standard diet weeks, they will be instructed to eat 100-150 grams of carbohydrates per day during the transition week. If they eat less than 200 grams per day of carbohydrates we will instruct them to eat 75-125 grams of carbohydrates during the standard diet weeks, we will instruct them to eat 75-125 grams of carbohydrates per day during the transition week. Most people with diabetes know how to carbohydrate count, however we will review carbohydrate counting at the time of the transition. Carbohydrate counting will be taught using the "Choose Your Foods: Food Lists for Diabetes" written by the American Diabetes Association and the American Nutrition of Dietetics.

For the VLCD portion of the study, participants will be given an isocaloric diet with a goal carbohydrate intake of less than 20% carbohydrates per day (~100 grams per day) for adolescents and less than ~50 grams per day for adults at least 18 years of age. Guidelines will be provided for meals. Participants will also receive training on the treatment of hypoglycemia and be instructed to call the study team immediately in the case of severe hypoglycemia.

Visit 3: After at least 2 weeks on each of the very low carbohydrate study diets, participants will meet virtually with study staff to review isulin pump and CGM data. Insulin pump and CGM data will be uploaded (Tidepool, Dexcom, Medtrnoic, Omnipod or Tandem site, depending on the insulin pump being used) and reviewed virtually, as is commonly done in clinical practice. Dose adjustments will be made as clinically indicated. Participants will receive a link in their email to fill out the 3 surveys using Qualtrix.

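### The plan gives three inconsistent carbohydrate levels for the VLCD, so the pooled VLCD estimate can average two carbohydrate targets, one reaching beyond the plan's own definition

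*Combined protocol and SAP*

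**What the plan says.** All references are to the combined protocol and SAP, Section I.

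- **Item 4, Background.** A VLCD is "defined as limiting carbohydrate intake to 50 grams per day or less". This is the only definition of the term, and it has no age split.
- **Item 4, Research Plan, Table 1 (study diets).** The caption reads "Types of study diets and macronutrient content in each planned diet". The rows are "Standard | 25%+ | Not specified | Not specified", "High Protein VLCD | 11% | 54% | 35" and "High Fat VLCD | 11% | 23% | 66" (the last figure in each VLCD row is a percentage). Neither VLCD row is split by age.
- **Item 5, Visit 2, in Part 1 and again in Part 2.** The VLCD is to be isocaloric, with a "goal carbohydrate intake of less than 20% carbohydrates per day (~100 grams per day) for adolescents" and a ceiling of roughly 50 g/day from age 18.
- **Item 5, Participants.** Ages run from 13 to 25, with 10 to 20 people in total. "At least 4 adults over the age of 18 will be enrolled". People who cannot maintain the VLCD are replaced.
- **Item 13, Statistical Considerations.** In both parts the diets are compared by paired t-tests on sensor glucose measures, with no age stratum or covariate. Dietary composition from ASA24 is to be reported for each diet; no breakdown by age is mentioned.

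**The concern.** Three statements describe the same intervention and do not agree. Nothing in the text says that the definition or Table 1 is relaxed for participants under 18, and the adolescent goal appears in both parts, so it is not an isolated slip.

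The statistical consequence concerns what the estimate means. The tests pool participants given two different carbohydrate ceilings and call the result a VLCD effect. Some of those participants may follow their instructions exactly and still eat more carbohydrate than the protocol's own definition allows. The average then depends on the age mix, which is only loosely fixed.

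There is a second consequence for feasibility, the stated purpose of Part 1. Without one reference figure, it is open whether an adolescent at, say, 80 g/day has followed the diet or is a candidate for replacement.

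**Working it through.** The plan has no sample-size or power figure to reproduce on this point. The check is whether the three carbohydrate statements can describe one diet.

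**Inputs from the plan:** 50 g/day (Background); 11% (Table 1, both VLCDs); under 20%, about 100 g/day, for adolescents and under about 50 g/day for adults (item 5, Visit 2).

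**Assumptions:** 4 kcal per gram of carbohydrate; energy intake of 1,600 to 2,800 kcal/day. The plan gives neither.

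**Formula:** grams = share × kcal / 4.

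1. *Energy intake implied by the adolescent goal:* 100 × 4 / 0.20 = 2,000 kcal/day.
2. *The three levels at 2,000 kcal:* 11% is 0.11 × 2,000 / 4 = 55 g; 20% is 100 g; 50 g is 200 / 2,000 = 10%.
3. *Ratio of the shares:* 0.20 / 0.11 = 1.82, whatever the energy intake.
4. *Could energy intake close the gap?* 100 g is 11% only at 100 × 4 / 0.11 = 3,636 kcal/day. 20% is 50 g only at 50 × 4 / 0.20 = 1,000 kcal/day.
5. *Table 1 against the definition:* 11% equals 50 g at 50 × 4 / 0.11 = 1,818 kcal/day. Above that intake, the Table 1 diet itself exceeds the definition and the adult goal.

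| kcal/day (assumed) | 11% | 20% | 50 g as a share |
|---|---|---|---|
| 1,600 | 44 g | 80 g | 12.5% |
| 2,000 | 55 g | 100 g | 10.0% |
| 2,800 | 77 g | 140 g | 7.1% |

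6. *Protein and fat:* Table 1 gives 54 + 35 = 89% and 23 + 66 = 89%. At 20% carbohydrate only 80% is left, 9 points short. A participant near the adolescent ceiling therefore cannot be on either Table 1 diet.
7. *A compliant case outside the definition:* 80 g/day at 2,000 kcal is 320 / 2,000 = 16%. This meets the adolescent goal but neither the 50 g definition nor Table 1.
8. *Age mix, study-wide limits:* with the minimum of 4 adults, adolescents could be 10 − 4 = 6 of 10 or 20 − 4 = 16 of 20. The mean assigned ceiling would be (4 × 50 + 6 × 100) / 10 = 80 g or (4 × 50 + 16 × 100) / 20 = 90 g, against 50 g if all were adults. These are ceilings, not expected intakes.

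**The case against.** The best defence is that the texts do different jobs. The 50 g figure is background, cited to a review and followed by evidence in adults. Table 1 describes planned diet content. The Visit 2 text sets a goal for participants, is worded identically in both parts, and splits by age in a way that looks deliberate. Since under 20% is a ceiling, an adolescent on an 11% diet meets it. ASA24 intake will be reported, and diaries, meal photos and frequent calls will track what people eat. This is also a small pilot.

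Much of that stands. It softens the conflict without removing it: intakes of about 51-100 g remain compliant and outside the only definition given, and the planned intake report has no age breakdown to reveal this.

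Four stronger readings should be resisted.

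- *A reader might infer that mixing the targets biases the paired comparison.* It does not. Each participant is their own control.
- *A reader might infer that adolescents face almost no dietary contrast.* At 2,000 kcal the standard-diet floor of 25% is 125 g, only 25 g above the adolescent ceiling, against 70 g above the Table 1 diet and 75 g above the adult ceiling. That is a limiting case. The transition-week rules branch at 200 g/day on the standard diet; from 200 g, the gaps to the two ceilings are 100 g and 150 g. The hypothesis "Decreased carbohydrate intake will lead to less postprandial hyperglycemia" also states a direction, not a size or a dose-response.
- *A reader might infer that adolescents will be the majority.* The 6 of 10 and 16 of 20 are study-wide limits. The minimum of 4 adults is not allocated to a part, so the mix in either part's analysis is unknown.
- *A reader might infer that only the adolescent goal is out of line.* Table 1 and the 50 g figure also separate for adults above about 1,818 kcal/day.

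**Conclusion.** The inconsistency is real and should be fixed. It limits interpretation; it does not invalidate the test. The adolescent ceiling is 1.8 times Table 1's carbohydrate share at any energy intake, and twice the 50 g definition when its gram figure is used. Energy intake would have to be about 3,636 kcal/day for 100 g to equal 11%, or 1,000 kcal/day for 20% to equal 50 g, so rounding does not explain the gap. As written, the pooled VLCD estimate can average two carbohydrate targets in a proportion set only by a study-wide minimum of 4 adults.

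Confidence is high for the textual mismatch. Its effect on the glucose results cannot be sized from the documents, because they give no achieved intakes, energy levels or age mix by part. The gram figures rest on 4 kcal/g and the assumed energy range; the share ratio and the 89% argument do not.

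**What to change.** 1. The investigators must reconcile the Background definition, the study-diet Table 1 and the Visit 2 goals in both parts. Which level is right is for them to decide.
2. Use the reconciled figure as the reference wherever the plan speaks of following or maintaining the VLCD, including the replacement rule.
3. From the ASA24 data already planned, report achieved carbohydrate in g/day and as a percentage of intake, on the standard diet and on the VLCD, for participants under 18 and for those 18 or older.
4. Show the paired differences for these two age groups beside the overall result, as descriptive estimates without tests.
5. Word the conclusions by the carbohydrate level achieved, not by the VLCD label alone.

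The cost is protocol wording and a small descriptive table, with no new data. The drawback is precision: with about 10 participants per part, the age-group estimates will be imprecise and one group may be very small.
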